10.7.3 Secondary and Exploratory Analyses

Acceptability:

Acceptability endpoints will be summarized by assessment time point using descriptive statistics (e.g., frequencies, means), as appropriate. We will compare ratings of key acceptability measures over time (e.g., prior to use, after Stage 1, and after Stage 2 use), assessing whether they changed with increased experience with product insertion using a one-sample t test. In addition, we will examine differences based on the assigned timing of insert use (i.e., 1 hour vs. 4 hours; pre coitus vs. post coitus) and between females and males, overall and within-couples.

Qualitative Analysis:

Qualitative analyses from the MATRIX-004 study will use a variety of techniques to provide an in-depth characterization of the contextual factors that affected participants' experience with product use during sex. The primary source of qualitative data used in the analysis will consist of raw textual data. Qualitative data will be audio-recorded, translated and transcribed in English, and coded for thematic analyses using Dedoose or a similar qualitative software. Data coding will be used as a primary analytical approach for data reduction; that is, to summarize, extract meaning, and condense the data. Whenever possible, we will also compare study sites and explore differences or similarities related to product use experiences due to different socioeconomic, cultural and geographical contexts, with a particular focus on male and female perspectives. The findings and interpretations of the data will be critically discussed until there is group consensus on the dominant themes and meanings contained in the data. Whenever possible, site staff will be involved to corroborate findings from the analysis team.

10.7.4 Missing Data

All attempts will be made to avoid missing data. However, missing values will remain as missing, i.e., no attempt will be made to impute. In general, only observed values will be used in data analyses and presentations. The one exception to this is summarizing concentration data; values that are detectable but below the lower limit of quantification (LLOQ) will be set to one-half the value LLOQ; concentrations below the limit of detection will be set to 0. Otherwise, no imputation is anticipated. No transformation will be applied.

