2.5 Clinical Studies of TAF/EVG Insert

2.5.1 Pharmacokinetics

[figure not shown]
In the first-in-woman study (CONRAD 146),²⁸ 16 healthy, 18-50 year old, HIV-uninfected women in the US used one TAF/EVG (20/16mg) vaginal insert and were randomized (1:1) to sample collection time groups for up to 7 days post dosing. In Group 1, participants were randomized to have tissue sampling obtained at 4 and 48 hours versus 24 and 72 hours post insert use for Group 2. All participants had plasma, VF and vaginal tissue collected for PK of TAF, EVG, TFV and TFV-diphosphate (TFV-DP).

Systemic plasma exposure was low, consistent with topical delivery. Mucosal concentrations were high and prolonged, with mean and median TFV VF concentrations exceeding 200,000 ng/mL and 1,000 ng/mL for up to 24 hours and 7 days post dosing, respectively. All participants had vaginal tissue EVG concentrations of > 1 ng/mg at 4 and 24 hours post dosing. The majority had tissue TFV-DP concentrations exceeding 1000 fmol/mg by 24 – 72 hours post dosing.

TFV, TAF and EVG in Vaginal Fluid s/p Single Dose

TFV-DP and EVG concentrations in CV tissue after single dose

MATRIX-001, a phase I safety and PK study, is currently enrolling 60 healthy 18-50 year old women across 3 sites in Kenya, South Africa, and the US. Participants are randomized (1:1) to

apply a placebo or TAF/EVG insert vaginally for 3 consecutive days then every other day for 14 days. (ClinicalTrials.gov NCT06087913)

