10.4 Sample Size and Power Calculations

Based on previous findings on the impact of sex on TFV vaginal gel from MTN-011¹⁸ and focusing on observed differences in TFV-DP concentrations in vaginal tissue, we would need about 20 female participants (10 per group) to detect a similar effect size (~65%) with 80% power at a 0.05 significance level. We are planning to enroll 32 couples to complete at least 28 to provide sufficient power to analyze effect differences per site. Altogether, this sample size will provide 80% power to detect a minimum of 55% difference in TFV-DP concentration (effect size) at 5% level of significance.

Qualitative data collection

Up to 40 study participants (6-10 female and 6-10 male per site) will be purposively selected and invited to complete an IDI after V8 but before exiting the study.

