10.7.2 Primary Analysis(es)

PK and PD:

PK analysis will include descriptive statistics by sample time point of EVG, TFV, and TAF concentrations for all plasma, CVT, and CVF sample types, in addition to TFV-DP concentrations from CVT samples.

PD endpoints will be summarized using descriptive statistics by time point as well as changes from baseline. Estimates and 95% confidence intervals will be provided.

Comparisons:

- At baseline: Compare the 1-hour pre/post coitus and 4-hour pre/post coitus groups to ensure groups are comparable
- At stage 1 (pre coitus)
 - For the 1-hour group: comparing 5 hours after coitus (6 hours after insert) to the 6 hours after insert at baseline
 - For the 4-hour group: comparing 2 hours after coitus (6 hours after insert) to the 6 hours after insert at baseline
- At stage 2 (post coitus)
 - For the 1-hour group: comparing 7 hours after coitus (6 hours after insert) to the 6 hours after insert at baseline
 - For the 4-hour group: comparing 10 hours after coitus (6 hours after insert) to the 6 hours after insert at baseline

Statistical Analysis plan:

Categorical variables will be summarized by frequencies and percentages. Continuous variables will be summarized by mean (SD) when found normally distributed. Median (IQR) will be used otherwise. Normality will be assessed graphically by Q-Q plots and statistically by Shapiro-Wilk test for normality.

To assess for the comparability between the two groups of the study at baseline, t-test or Mann-Whitney test will be used (based on the normality assumptions) to assess for the differences in continuous variables. Chi-squared test for independence or Fisher's exact test will be used for categorical variables as appropriate.

For the 1-hour pre/post coitus insert group, Paired analysis will be conducted for each endpoint at 6 hours post insert for stage 1 and stage 2 to compare to the baseline separately. For this analysis paired t-test or Wilcoxon signed rank test will be used as appropriate. Similar analysis will be conducted for the 4-hour pre/post coitus insert group.

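### The plan bars any transformation, so the mixed model, which has no rank fallback, runs on raw concentrations although the trial is sized on a percentage difference; the power lost depends on a spread the protocol does not give

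*Protocol*

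**What the plan says.** - **Scale and non-detects (Protocol 10.7.4).** Detectable values under the LLOQ become half the LLOQ, and "concentrations below the limit of detection will be set to 0". The section then ends, without restriction: "No transformation will be applied".
- **Choice of test (10.7.2).** "Normality will be assessed graphically by Q-Q plots and statistically by Shapiro-Wilk test for normality". The result decides between paired t and Wilcoxon signed rank for each stage against baseline, and between repeated-measures ANOVA and Friedman across V3, V6 and V9.
- **Final model (10.7.2).** A mixed effect model compares the 1-hour and 4-hour groups, and each group with its baseline. No non-parametric alternative is named for it.
- **Sizing (10.4).** For the anchor effect, "we would need about 20 female participants (10 per group") are said to suffice "to detect a similar effect size (~65%) with 80% power at a 0.05 significance level". Then: "We are planning to enroll 32 couples to complete at least 28", giving "80% power to detect a minimum of 55% difference in TFV-DP concentration (effect size) at 5% level of significance".
- **Variability.** No SD, CV or other measure of spread is given for any concentration.

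**The concern.** The sizing question is relative: by what fraction does coitus change the concentration? The model fixed by the protocol is additive. Suppose both groups have the same 55% reduction, but sample baseline means m and k·m. The raw changes are 0.55m and 0.55km, so an additive model reports a group difference of 0.55m(k − 1) where the ratio is 0.45 in both. With right-skewed data, raw means and their standard errors are also driven by the few women with the highest values.

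The primary hypothesis (10.3) is of no clinically significant change, so lost power makes a non-significant result more likely and easier to read as support. The two clauses of 10.7.4 also lock together: a value of 0 has no logarithm, so the scale cannot be changed without changing the non-detect rule.

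**Working it through.** **1. Reproduce the figure in 10.4.** Inputs: 65% at 10 per group, 80% power, 5% (sidedness not stated; two-sided assumed), 28 completers = 14 per group.

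Raw percentage scale, two-sample normal formula:
- Implied SD = 0.65 / [(1.960 + 0.842) × √(2/10)] = 0.519 of the mean.
- Detectable difference at 14 per group = 0.65 × √(10/14) = 0.549. This matches the stated 55%.

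Log scale, same anchor:
- −ln(0.35) = 1.050, and 1.050 × √(10/14) = 0.887.
- Detectable reduction = 1 − e^(−0.887) = 0.588, about 59%.
- Implied log SD = 1.050 / [2.802 × √(2/10)] = 0.838. Power for 55% is then Φ(0.799 / (0.838 × √(2/14)) − 1.96) = Φ(0.56) = 71%.

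**2. Choose a range of spread.** All of these are assumptions.
- 0.49 = √ln(1 + 0.519²): the raw reading that reproduces 55%.
- 0.63 = √ln(1 + 2 × 0.519²/(1 + 0.35²)): the same reading with constant CV.
- 0.79 = 1.050/1.325, where 1.325 is the standardised effect that a t-test detects at 10 per group: the log reading.
- 1.0 and 1.2: wider values, with no basis in the protocol.

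**3. Simulate.** Log-normal Stage 0 and Stage 1 values, true ratio 0.45 in both groups, 14 per group, two-sided 5%. The model contrast is stage against baseline within one group, with variance pooled over both groups (26 df); 20,000 trials per cell. The paired columns use 4,000 trials. Each cell gives power at correlation 0.3 / 0.5.

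| Log SD | Model, raw | Model, log | Paired, test chosen by Shapiro-Wilk | Paired, log t |
|---|---|---|---|---|
| 0.49 | 98.6 / 99.6 | 99.9 / 100 | 99.4 / 99.9 | 99.6 / 100 |
| 0.63 | 88 / 94 | 97 / 99.5 | 92.5 / 98 | 96 / 99 |
| 0.79 | 66 / 75 | 87 / 95 | 76 / 88 | 84 / 94 |
| 1.0 | 41 / 50 | 68 / 82 | 55 / 68 | 65 / 79 |
| 1.2 | 27 / 32 | 53 / 67 | 41 / 52 | 50 / 64 |

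With no coitus effect, every version rejected about 4–5% of the time.

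**4. Three-stage check.** This uses Stages 0, 1 and 2 with compound symmetry, 14 per group and a 55% reduction. Spread is given as between-woman/within-woman log SD.
- 0.5/0.5: 99% log against 92% raw; 99% against 81% if only one group is affected.
- 0.7/0.7: 85% against 62%; 84% against 43% if only one group is affected. The group-by-stage contrast in that last case has 54% against 27%.
- 1.0/0.7: 85% against 49%.
- 0.35/0.35: no loss at 55% in the planned comparisons.

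For V3/V6/V9, where tissue TFV-DP is measured, 0.7/0.7 gives 85% for log repeated-measures ANOVA and 69% for the planned rule, which nearly always selects Friedman.

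**5. Contribution of the other rules (0.7/0.7, paired).** The Shapiro-Wilk step costs 1–2 points against always using Wilcoxon. With 5% or 20% of baseline values below detection, log against planned rule is 75% against 67%, then 67% against 61%. Without non-detects it is 79% against 68%, so the zeros do not widen the gap.

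**The case against.** The strongest reply is that the loss is unproven and may be small. The protocol gives no spread, and at the spread that reproduces its own 55% (log SD 0.49) almost nothing is lost. Wilcoxon, Mann-Whitney and Friedman are already available when normality fails, and median (IQR) is used for summaries. All of this stands, and it limits the size of the point. It does not reach the mixed model, and it does not make a raw difference estimate a percentage.

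It can also be said that the sentence closes a section on missing data, that the zero rule is introduced for summarising concentrations, and that a statistical analysis plan may specify the model. As worded, however, the ban is unlimited, so a later plan using logs would contradict the protocol.

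Section 10.4 also reproduces if 65% and 55% are read as standardised paired effects (0.65 with 20 women gives 79%, 0.55 with 28 gives 80%). The section calls the figure a difference in concentration, so the percentage reading is the plain one, but the text should settle it.

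Three stronger inferences are tempting and are not supported:
- **That the protocol shows high skew.** Section 2.5.1 reports "mean and median TFV VF concentrations exceeding 200,000 ng/mL and 1,000 ng/mL for up to 24 hours and 7 days post dosing". That contrast describes decline over time. It says nothing about spread between women at one time, and the planned comparisons match on time since dosing.
- **That 10.4 implies a log SD of 0.79.** That value comes from the log reading, which gives a detectable difference of about 59% at 14 per group and so does not reproduce the stated 55%.
- **That the normality pre-test or the zeros cause much of the loss.** Step 5 shows that they add little. The zero rule matters because it blocks a log analysis.

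**Conclusion.** The point holds in a limited form. The protocol fixes a raw-scale mixed model, with no rank fallback, for an effect that it sizes as a percentage. The mismatch in what is estimated follows from the text and needs no assumption about spread.

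The power loss does depend on spread. If concentrations are log-normal, with 14 per group, a 55% reduction in both groups and correlation 0.3–0.5, the model contrast loses about 0–1 points at log SD 0.49, 6–9 at 0.63, 20 at 0.79 and 25–35 at 1.0–1.2. The paired route loses about 0–3 points at 0.49–0.63, 6–8 at 0.79 and 8–12 at 1.0–1.2. This is a loss of efficiency and interpretability; Type I error under no coitus effect is sound.

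**What to change.** 1. Replace the last sentence of 10.7.4 with: *Concentrations will be analysed on the natural-log scale and reported as geometric mean ratios with 95% CIs.* Apply it to the mixed model and to the paired and repeated-measures comparisons.
2. In these analyses, treat values below the LLOQ as left-censored, or set them all to one positive value such as LLOQ/2 with a sensitivity analysis. Do not use 0. Where most values are below the LLOQ, report the proportion quantifiable.
3. Keep Wilcoxon and Friedman as pre-stated sensitivity analyses, so that a normality test no longer selects the primary method.
4. In 10.4, say that the effect is a percentage and restate it on the log scale: about 59% at 14 per group from the same 65% anchor.

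The cost is a wording change, slightly more work for censored values, and a slightly less favourable stated detectable difference. It should be made before concentrations are analysed; made later, the choice of scale would look data-driven.

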11 DATA HANDLING AND RECORDKEEPING

11.1 Data Management Responsibilities

Data collection tools will be developed by the DM(s) in conjunction with the protocol team. Quality control and data integrity are managed manually and systematically with reports and queries routinely generated and provided by the DM(s) to the study sites for verification and resolution. As part of the study activation process, each study site will identify all CRFs to be used as source documents. Study CRF data will be entered and cleaned using a data management system compliant with the ICH Good Clinical Practices (GCP) and US CFR guidelines for electronic data capture.

IDI files generated in the field will be electronically transferred to RTI International using a secure File Transfer Protocol (FTP) site, where they will be uploaded and managed using a qualitative software package. RTI International will act as a hub and manage all qualitative data for the study. A convention for file naming will be developed, and all data will be labeled according to this process. Transcripts will be transferred to RTI International as they are completed. RTI International will save all versions of all files on a secure, password-protected server in the US.

11.2 Source Documents and Access to Source Data/Documents

All study sites will maintain source data/documents in accordance with MATRIX's Good Documentation Practice (GDP) guidelines (www.matrix4prevention.org).

Each IoR/designee will maintain, and store securely, complete, accurate and current study records throughout the study. In accordance with U.S. regulations, for the investigational products tested, IoRs/designees will maintain all study documentation for at least two years following the date of marketing approval for the indication in which they were studied. If no marketing application is filed, or if the application is not approved, the records will be retained for two years after the investigation is discontinued, or longer as per local regulatory requirements, and the US FDA is notified.

Study records must be maintained on site for the entire period of study implementation. Thereafter, instructions for record storage will be provided by CONRAD. No study records may be moved to an off-site location or destroyed prior to receiving approval from CONRAD.

11.3 Quality Control and Quality Assurance

Study sites will conduct quality control and quality assurance procedures in accordance with MATRIX's Quality Management Plan (www.matrix4prevention.org).

12 CLINICAL SITE MONITORING

Study monitoring will be carried out by ACRO for African sites and by CRA Resources for US sites. Study monitors will do the following:

- Review informed consent forms, procedures, and documentation
- Assess compliance with the study protocol, ICH GCP guidelines, and applicable regulatory requirements (US and non-US), including US Code of Federal Regulations (CFR) Title 45 Part 46 and Title 2 Parts 200 and 225
- Perform source document verification to ensure the accuracy and completeness of study data
- Verify proper collection and storage of biological specimens
- Verify proper storage, dispensing, and accountability of investigational study products
- Assess implementation and documentation of internal site quality management procedures

Monitoring visits may be conducted on-site or remotely. Remote visits may include remote source document verification using methods specified for this purpose. Remote monitoring visits may be performed in place of or in addition to onsite visits to ensure the safety of study participants and data integrity.

For on-site visits, the IoR/designee will allow study monitors to inspect study facilities and documentation (e.g., informed consent forms, clinic and laboratory records, other source documents, CRFs), as well as observe the performance of study procedures. The IoR/designee also will allow inspection of all study-related documentation by authorized representatives of MATRIX, CONRAD, USAID, FDA, OHRP, IRBs/IECs/DRAs and other local, US, or international regulatory authorities. A site visit log will be maintained at the study site to document all visits.

13 HUMAN SUBJECTS PROTECTIONS

Site investigators will make efforts to minimize risks to participants. Participants and study staff members will take part in a thorough informed consent process. Before beginning the study, IoRs/designees will have obtained IRB/IEC approval and the protocol will have been submitted to the FDA and other applicable national drug regulatory authorities. IoRs/designees will permit audits by USAID, the FDA, OHRP, MATRIX, IRBs/IECs/DRAs, and other local, US, or international regulatory authorities or any of their appointed agents.

Changes to this protocol may be implemented by investigators prior to IRB/IEC approval, if those changes are required to eliminate apparent immediate hazards to the study participant; see 45 CFR 46.108(a)(3)(iii) under the 2018 Requirements (<https://www.ecfr.gov>). These changes must be documented as Protocol Deviations and reported to the Protocol Team and IRBs/IECs as soon as possible; see ICH E6(R2), Good Clinical Practice, Section 4.5.4 (<https://www.fda.gov/science-research/clinical-trials-and-human-subject-protection/ich-guidance-documents>). In the event of a public health emergency, investigators should adhere to the recommendations of their local institutions, IRBs/IECs and local health departments. When conflicts exist between local directives, MATRIX, Protocol Team and/or USAID policies or guidance, sites should follow the requirement that is most protective of study participants and site staff.

13.1 Institutional Review Boards/Ethics Committees

The participating institution is responsible for assuring that this protocol, the associated site-specific informed consent forms (ICFs), and study-related documents (such as participant education and recruitment materials) are reviewed by an IRB/IEC responsible for oversight of research conducted at each study site and, as required, by applicable national DRA. Any amendments to the protocol must be approved by the responsible IRBs/IECs and (if applicable) national DRA prior to implementation.

Subsequent to the initial review and approval, the responsible IRBs/IECs must review the study at least annually. Each IoR/designee will make safety and progress reports to the IRBs/IECs at least annually and within three months after study termination or completion. These reports will include the total number of participants enrolled in the study, the number of participants who completed the study, all changes in the research activity, and all unanticipated problems involving risks to human subjects or others. In addition, the results of all ISP reviews of the study will be provided to the IRBs/IECs.

13.2 Protocol Implementation

Prior to implementation of this protocol, and any subsequent full version amendments, each site must have the protocol and the protocol consent forms approved, as appropriate, by their local IRBs/IECs and any other applicable regulatory entities. Upon receiving final approval, sites will submit copies of all relevant protocol/amendment documents (i.e., IRB/IEC approval letters with a detailed list of approved documents, approved ICF documents, etc.) to the MATRIX Clinical Trials Hub Regulatory team.

The MATRIX CRM(s) will review the submitted document packet to ensure receipt of all required protocol/amendment documents prior to study activation at the sites. Sites will receive a Study Activation Notification from the MATRIX CRM(s) that indicates successful completion of the protocol readiness process. A copy of the Study Activation Notification should be retained in the site's regulatory files.

Upon receiving final IRB/IEC and any other applicable approval(s) for a protocol/amendment, sites are required to submit copies of all relevant protocol/amendment documents (i.e., IRB/IEC submission letters, IRB/IEC approval letters with a detailed list of approved documents, related correspondence with IRB/IEC, approved ICF documents, etc.) to CONRAD prior to study activation. Upon receiving final IRB/IEC and any other applicable approval(s) for an amendment, activated sites should implement the amendment immediately but are still required to submit copies of all relevant amendment documents to CONRAD.

13.3 Study Coordination

CONRAD holds the Investigational New Drug (IND) application for this study. Delegation of any sponsor responsibilities for this study will be specified in writing between CONRAD and MATRIX.

Study implementation will be directed by this protocol, which may not be amended without prior written approval from the Protocol Co-Chairs and Protocol Team representatives from MATRIX and USAID. Study implementation will also be guided by a common SSP Manual that provides

further instructions and operational guidance on conducting study visits; data and forms processing; specimen collection, processing, and shipping; AE assessment, management and reporting; dispensing study products and documenting product accountability; and other study operations. Standardized study-specific training will be provided to sites by the MATRIX CRM(s) and other designated members of the Protocol Team.

Close coordination between protocol team members is necessary to track study progress, respond to queries about proper study implementation, and address other issues in a timely manner. The PSRT will address issues related to study eligibility and AE management and reporting as needed to assure consistent case management, documentation, and information-sharing across sites. Rates of accrual, adherence, follow-up, and AE incidence will be monitored closely by the team as well as the ISP and the MATRIX Clinical Trials Hub.

